## Risks and adverse events

In this context, adverse events will be any unintended symptoms or findings during examination, or severe increase in pain intensity during testing, to such extend that testing can't continue. In the case of adverse events, the data relevant to the participant will be excluded, and a new participant enrolled. A participant that can't continue due to pain intensity will be treated with caution and observed for potential pain increase. If needed, they will be set in contact with a medical doctor from the orthopedic department, at Hvidovre University Hospital and still receive treatment/compensation. 48 hours after testing, a phone consultation will be made, to make sure that the pain intensity has decreased.

If problems with equipment or testing should occur to such an extent that test protocol can't continue, a new date will, if possible, be set. Or else a new participant will be enrolled, and treatment/compensation is provided to the former participant.

In the case of unintended unblinding during testing (if allocation is revealed to HS), the data will be excluded from the collection due to risk of bias. If possible, a new set of participants (case and control) will be included, otherwise, subgroup analysis with participants with breach of blinding omitted will be performed.

An expected result from the test protocol is temporary pain and muscle soreness from the muscle force tests, in both cases and controls. Furthermore, an increase in symptoms from Osgood-Schlatter may be present after testing, in the case group. To our knowledge, this presents no safety hazard to the participants.

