## Hypotheses

The hypotheses being tested are

1. that adolescents with Osgood-Schlatter, has a lower knee extension RTD in their affected knee compared to matched controls
2. that adolescents with Osgood-Schlatter, has a lower knee extension RTD in their affected knee compared to their potential asymptomatic knee
3. that adolescents with Osgood-Schlatter, has a lower knee extension RTD in their potential asymptomatic knee compared to matched controls
4. that adolescents with Osgood-Schlatter, has a lower knee flexion RTD in their affected knee compared to matched control
5. that adolescents with Osgood-Schlatter, has a lower knee flexion RTD in their affected knee compared to their potential asymptomatic knee
6. that adolescents with Osgood-Schlatter, has a lower knee flexion RTD in their potential asymptomatic knee compared to matched controls
7. That levels of either early or late rate of torque development is negatively correlated with pain during rate of torque development-testing, countermovement jump height or power, anterior knee pain provocation test score, current pain, pain duration, KOOS child 'Pain', 'Sport/rec' or 'QoL' subscales,

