## Methods

### Study design

In this study we will include adolescent participants with Osgood-Schlatter, presenting as anterior knee pain localized to the tibial tubercle (OSD-group), and a matched group of pain free controls (control group), matched on sex, age (<1 year group difference) and type of sports (weightbearing vs non-weightbearing). The study will be conducted at the International Olympic Research Center - Copenhagen (Sports Orthopaedic Research Centre - Copenhagen), at Hvidovre University Hospital. The project will be initiated March 2023, with recruitment of 26 participants: 13 participants in the OSD-group, and 13 in control group.

Approval has been obtained from the ethical review board of the Capital Region of Denmark (H-20072873), and the Data Management Agency of Capitol Region of Denmark (P-2021-73).

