#### Clinical examination and treatment

The study procedures will be conducted by two examiners (JL and HS). JL will be aware of the case status and conducts the screening and preliminary testing. To avoid bias, examiner HS will be blinded for the case status during trial and will not know the Numerical pain Rating Scale-scores (NRS, 0-10, 'no pain' to 'worst pain imaginable') of the participants during testing. To strengthen the inter-reliability, the examiners will not change roles during the study.

The session starts with JL examining the potential participant in the OSD-case group, for Osgood-Schlatter. If the Osgood-Schlatter diagnosis is made, the participant is then enrolled. For the potential participant in the control group, JL screens for potential injury or pain in relation to the knee joint. In the absence of relevant pathology, the control-participant is enrolled.

Then, JL measures length of the lever arm and variables for peak hight velocity assessment. Participants will then answer the patient-reported outcome measures together with their parent/guardian.

For the rate of force development tests, HS will enter the room and conduct the tests as described below. For each attempt the participant will write down their NRS-rating on a piece of paper, out of sight from HS.

Before the rate of force development test is conducted, the participants are told that they can always abort the test, if they perceive that pain rises to such a degree that they can't continue the

testing, or they start feeling fearful or uncertain of their symptoms. They are ultimately told that potential pain felt during testing are not harmful and will subside within 24 hours, as is our experience from multiple earlier conducted tests.

HS leaves the room, for JL to conduct the Anterior Knee Pain Provocation test and save the NRS results.

HS returns to conduct the Counter Movement Jump Test, again blinded for the participants NRS-scores, which are written down on a piece of paper. HS leaves the room, and JL either treats the patient (case-group) or hands out compensation for participating (control-group).

Cases and controls will be instructed not to take any pain medication 24 hours prior to any assessment to ensure that this does not affect measurements.

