#### Anterior knee pain provocation test

The anterior knee pain provocation test is a unilateral self-performed and self-rated test, designed to provoke known anterior knee pain. Only the affected or most affected knee is tested. In the control group, the “affected leg” is decided by coin toss.

The participant will be instructed to *stand on the affected leg, with the non-affected side against the wall, and their back straight*. The back of the hand is held against the wall as support. They will then be instructed to stand in a static single-legged squat position, with knee flexion about 60°, while the other leg is extended forward above the ground. The position is held for 45 sec and timed with a stopwatch. Standardized verbal instruction is provided before each trial by the tester: *are you ready to start the test? Start... and stop.*

Participants will provide their perceived pain intensity immediately before and after completing the 45s. hold.

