### Outcome measures

The outcome measures are rate of torque development and NRS-values in relation to the force-measurements. To calculate the rate of torque (Nm/s/kg), the rate of force development-variables (N/s) is multiplied with length of the lever (m) and divided with the participant's bodyweight (kg).

Outcome variables related to the specified hypotheses are rate of torque development during 0-100 ms, 0-200 ms, peak RTD, and time to peak force during knee extension and knee flexion for both cases and controls.

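### Excluding and replacing participants whose testing is stopped by pain selects the analysed sample on an outcome, probably mainly among cases; the likely effect is modest and the recorded data can be kept

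*Combined protocol and SAP*

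**What the plan says.** Under Risks and adverse events, the definition of an adverse event includes a "severe increase in pain intensity during testing, to such extend that testing can't continue". The consequence follows: "In the case of adverse events, the data relevant to the participant will be excluded, and a new participant enrolled". The natural reading is that the whole participant leaves the data set.

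Under Outcome measures: "The outcome measures are rate of torque development and NRS-values in relation to the force-measurements". Hypothesis 7 expects that RTD "is negatively correlated with pain during rate of torque development-testing".

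Clinical examination and treatment fixes the order of the session. RTD testing comes first. The blinded examiner then leaves so that the other examiner can proceed "to conduct the Anterior Knee Pain Provocation test and save the NRS results", and the jump test comes last. The provocation test is described as "designed to provoke known anterior knee pain".

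For accidental unblinding the same section also excludes and replaces, but with a fallback if replacement is not possible: "otherwise, subgroup analysis with participants with breach of blinding omitted will be performed". For pain stops, no section keeps partial data, asks for counts by group or plans a sensitivity analysis.

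**The concern.** An exclusion triggered by extreme pain during testing is triggered by an extreme value of an outcome. By the plan's own reasoning, that outcome tracks RTD: besides hypothesis 7, the rationale suggests that local pain limits rapid maximal contraction. The participants removed would then tend to be those with the lowest RTD.

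The two groups are unlikely to be affected equally. Cases must have had pain for at least 12 weeks and have tubercle pain on loading. Controls are pain free and screened for knee pathology. The plan expects temporary soreness in both groups, but an increase in Osgood-Schlatter symptoms only in cases.

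Three things are at stake:

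- Pain during testing is understated in cases. This does not depend on any correlation with RTD.
- Hypothesis 7 loses the painful end of its range.
- If hypothesis 7 holds, the affected-knee extension difference (hypothesis 1) is pulled toward zero.

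In addition, a stop at the provocation or jump test would, as the rule is worded, discard RTD data already complete for both limbs and both movements. Because replacement restores 13 per group, nothing in the planned reporting would reveal any of this.

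**Working it through.** **Inputs from the plan (Sample size).** Means 6 and 3 Nm/kg/s at 0-100 ms, SD 2.6 (stated for asymptomatic adolescents, applied here to both groups), two-sided t-test, alpha 5%, 80% power, 13 per group.

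**The plan's own figure.** d = 3/2.6 = 1.154. The noncentral t calculation gives n = 12.83, rounded up to 13 per group; power at 13 is 80.6%. The stated sample size reproduces and is not in dispute.

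**Assumed, because the documents do not give them.** The proportion q of cases whose testing stops (5% or 10%), and the pain-RTD correlation rho in cases (-0.3, -0.5, -0.7). Pain and RTD are bivariate normal in cases, the most painful fraction q is removed and replaced, and no control is removed.

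**Shift in the difference.** With c = z(1-q), lambda = phi(c)/(1-q):

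- q = 5%: c = 1.645, lambda = 0.1031/0.95 = 0.109
- q = 10%: c = 1.282, lambda = 0.1755/0.90 = 0.195

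Expected difference = 3 - |rho| x 2.6 x lambda. The truncated pain variance is v = 1 - c x lambda - lambda^2 (0.810 at 5%, 0.712 at 10%), and the retained case SD is 2.6 x sqrt(rho^2 x v + 1 - rho^2).

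| Cases stopping | rho -0.3 | rho -0.5 | rho -0.7 | Power, 13 per group |
|---|---|---|---|---|
| none | 3.00 | 3.00 | 3.00 | 80.6% |
| 5% | 2.92 | 2.86 | 2.80 | 79% to 77% |
| 10% | 2.85 | 2.75 | 2.65 | 77% to 73% |

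The standard error of the planned difference is 2.6 x sqrt(2/13) = 1.02. The shifts of 0.08 to 0.35 are therefore about 0.1 to 0.3 of a standard error.

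**Robustness.** If pain explains only half the variance in who stops, lambda is multiplied by sqrt(0.5): 2.94 to 2.86 at 5%, 2.89 to 2.75 at 10%. The normal model puts 12.4% of cases below zero; a gamma RTD distribution with the same mean and SD gives 2.93 to 2.87 and 2.88 to 2.75.

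**Pain ratings.** Mean pain in cases falls by lambda: 0.11 SD at 5% and 0.19 SD at 10% (0.08 and 0.14 with the noisier stopping).

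**Hypothesis 7.** Truncated correlation = rho x sqrt(v)/sqrt(rho^2 x v + 1 - rho^2). A true -0.50 becomes -0.46 at 5% and -0.44 at 10%. If tested within 13 cases, which is also an assumption, simulated power falls from 44% to 37% and 34%.

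**Chance that it arises.** 1 - (1-q)^13 is 49% at 5% and 75% at 10% for at least one stop among 13 cases.

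**The case against.** The strongest reply concerns size. Nothing in the documents anchors a 5% or 10% stop rate: the plan treats such stops as adverse events and reports, from the team's earlier tests, that test pain is not harmful and subsides within 24 hours. Even on the assumed inputs, the RTD bias is well below sampling error and conservative. It vanishes if nobody stops or the correlation is zero, and it would reverse if the correlation were positive. All of that stands.

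The hypothesis 7 figures also rest on an analysis that the plan does not describe. Statistical methods names no correlation method, and the hypothesis is not restricted to cases. A move from -0.50 to about -0.45 is small beside sampling error at 13 participants. That stands too, so these figures are only illustrative.

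A reader might infer that the rule undermines the study's main aim. The documents do not support that. Expected results and implications places the main interest in non-symptomatic limbs and knee flexion. Those data are lost when the whole participant is excluded, but no bias for hypotheses 3 to 6 has been estimated. Nor may one infer that only cases are affected: temporary pain is expected in both groups, and no rate is given for either.

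What the reply does not remove is the rule itself. It is explicit, it acts on a listed outcome, and no other section offsets it.

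**Conclusion.** The concern holds as a stated selection rule with a modest likely effect. It should be fixed because keeping data already recorded is cheap. Truncation of pain ratings follows whenever those excluded are those with high test pain. Weakening of hypothesis 7 needs a non-zero correlation, and understatement of the affected-knee extension difference needs a negative one. The sizes are conditional on the assumed stop rates and correlations, a common SD of 2.6 and no stops among controls. They show plausible scale and are not predictions. The sample size calculation is unaffected.

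**What to change.** Replace the exclusion sentence, for pain stops only, with a data-handling rule such as:

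> For eligible participants whose testing stops because of pain, RTD data and NRS ratings recorded before the stop are kept in the main analysis. An attempt broken off early is kept for each outcome whose time window it covers (for example 0-100 ms and 0-200 ms). The replacement is added to the same group and the original data are not deleted. The per-participant summary of attempts is the one used for everyone else, and the number of attempts behind each value is reported. Pain stops are reported by group, with the test at which they occurred. A sensitivity analysis is restricted to participants who completed testing. Participants found ineligible may still be excluded.

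Two tempting additions are best left out:

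- Requiring an attempt to last until the instruction to relax (about 3-4 seconds) would drop valid early RTD from the most painful attempts.
- Worst ranks for limbs left untested after a stop elsewhere would create deficits exactly where the study looks for central inhibition. In null simulations, adding two or three such cases to 13 raised the rank sum test's false-positive rate from a nominal 5% to roughly 7% and 9 to 10%.

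How three attempts become one value is a separate question of outcome definition and need not be settled here.

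The cost is one paragraph, a count by group and one short sensitivity analysis, with no recruitment beyond the replacements already foreseen. The case group may slightly exceed 13: expected extra cases are 13q/(1-q), or 0.7 at 5% and 1.4 at 10%. Some values will rest on fewer attempts.

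Recovery may be partial, because the affected leg is tested first and a limb with no attempt stays missing. At 10% stopping, if half of the stopped cases have a usable affected-knee extension attempt, mean pain among those analysed is (0.90 x -0.195 + 0.05 x 1.755)/0.95 = -0.092 SD. The difference is then 2.93 to 2.83, against 2.85 to 2.65 with exclusion, provided the kept attempts represent the missing ones.

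When testing stops and how participants are cared for do not change.
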